8.2.2. Secondary Analyses (Efficacy)

The following secondary endpoint analyses support the primary endpoints in the assessment of efficacy. All analyses in this section use the ITT analysis set only. Unless otherwise stated, efficacy data will be summarized up to Week 64, and analyzed up to Week 56.

0900177 (ed) 93181b656\Approved\Approved On: 08-10-2019 08:56 (GMT)

1. Other time points for the primary efficacy measures.

The ANCOVA model described above for the co-primary endpoints, using covariates of Baseline score, Baseline diary average pain, Index Joint, Highest KL grade (2, 3 or 4), NSAID cohort and Treatment, with Study Site as a random effect, will be used in the analysis of WOMAC Pain, WOMAC Physical Function and PGA for the change from Baseline to Weeks 2, 4, 8, 24, 32, 40, 48, and 56. This analysis will be produced using multiple imputation (as described in [Section 7](#) and [Section 8.1.1](#)), and BOCF and LOCF for missing data.

The MMRM analysis described above in [Section 8.1.1](#) will also analyze results for the secondary time points of Weeks 2, 4 and 8, for the co-primary efficacy endpoints.

The CMH test for the PGA with corresponding summary will be performed for the change from Baseline to Weeks 2, 4, 8, 24, 32, 40, 48, and 56, as described above for the primary PGA endpoint.

2. Secondary endpoints analyzed using ANCOVA.

The ANCOVA model described above for the primary endpoint using covariates of Baseline score, Baseline diary average pain, Index Joint, Highest KL grade (2, 3 or 4), NSAID cohort and Treatment, with Study Site as a random variable, will be used in the analysis of WOMAC Stiffness subscale, WOMAC Average score, WOMAC Pain item “Pain when walking on a flat surface”, WOMAC Pain item “Pain when going up or down stairs” for the change from Baseline to Weeks 2, 4, 8, 16, 24, 32, 40, 48, and 56. This analysis will be produced using multiple imputation for missing data.

The ANCOVA analysis (with covariates of Baseline diary average pain, Index Joint, Highest KL grade (2, 3 or 4), NSAID cohort and Treatment, with Study Site as a random variable) will be produced for the Average Pain in the Index Joint from the diary, for the change from Baseline to Days 1, 2, 3, 4, 5, 6, and 7, and to Weeks 1, 2, 3, 4, 6, 8, 10, 12, 16, 20, 24, 32, 40, 48, and 56, using multiple imputation for missing data.

3. Response and Incidence endpoints.

The response endpoints of OMERACT, improvement in PGA ≥ 2 and WOMAC Pain and Physical Function ≥ 30 , 50, 70 and 90% improvements are analyzed using logistic regression with covariates of Baseline score (WOMAC Pain for OMERACT), Baseline diary average pain, Index Joint, Highest KL grade (2, 3 or 4), NSAID cohort and Treatment Group, for response at Weeks 2, 4, 8, 16, 24, 32, 40, 48, and 56. These analyses use mixed BOCF/LOCF, and BOCF and LOCF for missing data. The use of BOCF for missing data implies subjects with missing data are included in the analysis as non-responders. Similarly the use of LOCF in the case where subjects have no post-Baseline data (and Baseline would be carried forward) again implies those subjects are included in the analysis as non-responders.

09001776e493781b6561Approved\Approved On: 04-Oct-2019 08:56 (GMT)

Incidence of rescue medication use will be analyzed using the logistic regression as described above up to Week 56, but only using LOCF imputation for missing data.

The incidence of treatment discontinuation due to lack of efficacy will be analyzed using logistic regression with model terms of Baseline WOMAC Pain, Baseline diary average pain, the three stratification parameters and treatment group, and using incidence up to the end of treatment period (the Week 56 visit or early termination). Discontinuation in the post-treatment safety follow-up period will not be included in this endpoint for analysis, but will be summarized as part of the safety tables. Lack of efficacy is indicated as ‘Insufficient Clinical Response’ on the Subject Summary Case Report Form. An additional analysis will be performed also including the discontinuation reason of ‘Patient meets protocol specified pain criteria for discontinuation’.

The cumulative WOMAC Pain and Physical Function response at Weeks 16, 24 and 56 using response definitions from a reduction of >0% to =100% (in steps of 10%) will be summarized, using mixed BOCF/LOCF, and also LOCF and BOCF imputation. Imputation with BOCF for subjects with missing data at that time point will lead to the subjects being assessed as non-responders for the response endpoint.

4. Time to Event.

The time to treatment discontinuation due to lack of efficacy will use the log-rank test. Survival curve estimates (time to 1st, 2nd, 5th, 10th and 25th percentiles, and minimum and maximum values) and a plot of the time to discontinuation (failure) will be shown using the Kaplan-Meier estimates. Only treatment discontinuation up to the end of treatment period (Week 56 visit or early discontinuation) will be used in this analysis. Discontinuation due to lack of efficacy after the end of treatment visit will be included in the standard safety tables. Imputation of time to event for discontinued subjects (discontinuing for reasons other than lack of efficacy) prior to the Week 56 visit uses censoring at the time of discontinuation. Imputation of time to event for completed subjects or discontinued subjects (for any reason) after the Week 56 visit uses censoring at the Week 56 visit time point. Lack of efficacy is indicated as ‘Insufficient Clinical Response’ on the Subject Summary Case Report Form. An additional analysis will be performed also including the discontinuation reason of ‘Patient meets protocol specified pain criteria for discontinuation’.

5. Number of Days and Amount of Rescue Medication Use.

The rescue medication data will be converted to Weekly scores for the week prior to the timepoint of interest. Calculation of the endpoints for both the IPAP and the concomitant medication log data collection is described in [Appendix 1.4](#).

The number of days and amount of rescue medication endpoints will be analyzed using the negative binomial model, with model terms for Baseline WOMAC Pain score, Baseline diary average pain, Index Joint, Highest KL grade (2, 3 or 4), NSAID cohort and Treatment Group as described in [Section 8.1.2](#).

090017764931816561Approved\Approved On: 08-10-2019 08:56 (GMT)

The number of days of rescue medication use per week endpoint will be analyzed for the Weeks 2, 4, 8, 16, 24, 32, 40, 48, and 56. The amount of rescue medication use per week will be analyzed for the Weeks 2, 4, 8 and 16. Missing data will be imputed using LOCF only. For this analysis, Baseline data will not be carried forward in the case of a post-Baseline observation not being available for use in LOCF.

6. EuroQol 5 Dimensions 5 Level (EQ-5D-5L).

The Baseline and Weeks 8, 16, 24, 40, 56 and 64 responses in the five dimensions (mobility; self-care; usual activities; pain/discomfort; anxiety/depression) and overall health utility score from the EuroQol 5 Dimensions 5 Level (EQ-5D-5L) will be summarized by treatment group. This summary will use observed data only (no imputation for missing data). The calculation of the overall health utility score is described in [Appendix 1.4](#).

An additional question, called the EQ-VAS asks the subject to rate their health today using a VAS scale from 0 (the worst health you can imagine) to 100 (the best health you can imagine). This will be summarized along with the health utility score. A table showing number and percentage of subjects will summarize the response for each dimension (item) of the EQ-5D at each time point. These summary tables will be shown by treatment group. In addition, for each treatment and each time point assessed, descriptive statistics (mean, standard deviation, median, number of subjects) will be shown for the health utility score, and the EQ-VAS measure of health today.

7. Work Productivity and Activity Impairment Questionnaire for Osteoarthritis (WPAI:OA).

The change from Baseline to Weeks 16, 24, 56 and 64 in the 4 impairment scores of the Work Productivity and Activity Impairment Questionnaire for Osteoarthritis (WPAI:OA) will be summarized by treatment group.

This summary will use observed data only (no imputation for missing data). The calculation of these endpoints is described in [Appendix 1.4](#).

The summary will show number and percentage of subjects with a decrease, no change, and an increase in score for the change from Baseline to each time point, as well as descriptive statistics (mean, standard deviation, median, number of subjects) of the Baseline and change at Weeks 16, 24, 56, and 64.

Change from baseline at Weeks 16, 24, and 56 in the 4 parameters will be analyzed using the ANCOVA model described above for the primary endpoint using covariates of the corresponding Baseline score, Baseline diary average pain, Index Joint, Highest KL grade (2, 3 or 4), NSAID cohort and Treatment, with Study Site as a random variable.

8. Health Care Resource Utilization.

The Health Care Resource Utilization data at Baseline, Weeks 64 and 80 will be summarized.

09001776e193781b6561Approved\Approved On: 08-10-2019 08:56 (GMT)

9. Treatment Satisfaction Questionnaire Medicine v.II (TSQM v.II).

The Weeks 16 and 56 responses in the 4 TSQM parameters of satisfaction with effectiveness, side effects and convenience, and overall satisfaction will be summarized. The 11 questions of the TSQM are used to calculate the 4 endpoints of Effectiveness, Side Effects, Convenience and Global Satisfaction, each scored on a 0-100 scale with 100 being the best level of satisfaction.

The four parameters of the TSQM will be analyzed using the ANCOVA model described above for the primary endpoint using covariates of the Baseline diary average pain, Index Joint, Highest KL grade (2, 3 or 4), NSAID cohort and Treatment, with Study Site as a random effect at both Weeks 16 and 56. Summary tables showing number and percentage of subjects by value and treatment group will be shown for the TSQM items 1-11, and the four satisfaction parameters.

This summary and analysis will use observed data only (no imputation for missing data). The calculation of these endpoints is described in [Appendix 1.4](#).

10. Patient Reported Treatment Impact Assessment-Modified (mPRTI) at Weeks 16 and 56.

The mPRTI is collected at Weeks 16 and 56. The two endpoints derived from this questionnaire are described below:

- Patient willingness to use drug again. This comes from the question “In the future, would you be willing to use the same drug that you have received in this study for your osteoarthritis pain?” This is rated on a 5 point Likert scale from 1 (‘Yes, I would definitely want to use the same drug again’) to 5 (‘No, I definitely would not want to use the same drug again’).
- Patient preference of drug versus prior treatment. This comes from the question “Overall, do you prefer the drug that you received in this study to the treatment you received before this clinical trial?” This is rated on a 5 point Likert scale from 1 (‘Yes, I definitely prefer the drug I am receiving now’) to 5 (‘No, I definitely prefer my previous treatment’).

The two parameters of the mPRTI will be analyzed using the CMH test (stratified by the combinations of the three stratification factors) at both Weeks 16 and 56. If there are too few subjects in any stratification combination group (defined as <15 in any strata level) then the analysis will be modified to an unstratified test. Summary tables showing number and percentage of subjects by value and treatment group will be shown for all mPRTI questions.

This summary and analysis will use observed data only (no imputation for missing data).

09001776e193181b656Approved\Approved On: 08-10-2019 08:56 (GMT)

11. Lower Extremity Activity Scale.

The LEAS is an 18-point scale ranging from 1 ('I am confined to bed all day') to 18 ('daily vigorous physical activity'), and is collected at Baseline and Weeks 4, 8, 16, 24, 56 and 80.

The number and percentage of subjects whose activity score is improved (increased), worsened (decreased) or have no change, and each level of change will be shown by treatment group for each week, using LOCF for any missing data. The mean (with standard deviation) and median change will also be summarized. The change from baseline to each post-Baseline visit (using LOCF for missing data), and for the worst change from Baseline (over all post-Baseline visits) will be summarized, and analyzed using CMH test (stratified by the combinations of the three stratification factors) (note, Week 80 data will be summarized, but not analyzed). If there are too few subjects in any stratification combination group (defined as <15 in any strata level) then the analysis will be modified to an unstratified test.

12. Accelerometry Endpoints.

The five accelerometry endpoints will be collected prior to Baseline (at least 4 days, with 1 being a weekend day) and prior to Weeks 16 and 56 (at least 8 days, with 2 being weekend days). The change from Baseline to Week 16 and 56 will be calculated for these parameters. Summaries and analyses of these endpoints will use observed data for change from Baseline to Weeks 16 and 56, and imputation using LOCF for Week 56.

These parameters will be analyzed using a negative binomial model using covariates of the corresponding Baseline accelerometry score, Baseline diary average pain, Index Joint, Highest KL grade (2, 3 or 4), NSAID cohort and Treatment.

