Formal sample size calculation was not peformed for the actigraphy data collection, as published actigraphy data in a clinical trial with matched population was not available. However, data from Farr (2008), where the mean minutes of moderate to vigorous physical activity in an OA population is approximately 24 minutes per day, with a standard deviation of 20. Assuming a standard deviation for the change from Baseline of 14 (using a Baseline to post-Baseline correlation of 0.75 to represent strong association in activity over 2 timepoints), then a sample size of 120 subjects per treatment group would give 79 and 91% power for treatment differences of 5 and 6 minutes respectively (approximately 20 and 25% of the Baseline mean shown in this paper).

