## 9.4.4.2. Actigraphy

Monitoring of physical activity level via actigraphy will be conducted in approximately 360 subjects.

A valid day of monitoring will be defined as 10 or more wear hours in a 24-hour period as verified from accelerometer output. During Screening, a complete monitoring period will be defined as containing at least 1 valid weekend day of data and a minimum of 4 valid days of monitoring. During activity level monitoring between Week 14 and the Week 16 visit and between Week 54 and the Week 56 visit, a complete monitoring period will be defined as containing at least 2 valid weekend days of data and a minimum of 8 valid days of monitoring.

An average daily activity count will be calculated for each subject. These data will then be sorted into three intensity thresholds: light, moderate and vigorous physical activity levels. The intensity count thresholds for each of these activity levels are described in the statistical analysis plan. The data will be further summarized as total daily time (minutes) for each intensity level. From these data the following parameters will be calculated:

- 1. Average daily physical activity counts.
- 2. Average daily minutes of physical activity.
- 3. Average daily minutes of moderate to vigorous physical activity (MVPA).
- 4. Average daily minutes of bouted MVPA. A "bout" is defined as 10 or more consecutive minutes above the moderate physical activity level threshold, with allowance for interruptions of 1 or 2 minutes below the threshold.
- 5. Average daily step count.

The change from Baseline to Week 16 and 56 will be calculated for these parameters. Summaries and analyses of these endpoints will use observed data for change from Baseline to Weeks 16 and 56, and imputation using last observation carried forward for Week 56.

These parameters will be analyzed using the Negative Binomial model, with model terms of Baseline activity score, index joint, Kellgren-Lawrence grade, NSAID cohort, and treatment group. Estimated levels of each activity parameter will be shown for each treatment group, and the ratio (with 95% CI) for comparisons versus NSAID will be shown.

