6.3.4. Activity Level Monitoring Endpoints

The Lower Extremity Activity Scale (LEAS) is an 18-point integer scale reflecting the subjects physical function status, ranging from 1 (bed bound) to 18 (competitive athlete).

The accelerometry endpoints of average daily minutes of physical activity, average daily physical activity counts, minutes of moderate to vigorous physical activity (MVPA), minutes of bouts MVPA, and average daily step count will be calculated from the raw data.

The Activity Level Monitoring endpoints are listed below:

- *Lower Extremity Activity Scale: change from Baseline to Weeks 4, 8, 16, 24, 56 and Week 80 (all subjects).*
- *Change from Baseline to Weeks 16 and 56 in average daily minutes of physical activity (a subset of subjects).*
- *Change from Baseline to Weeks 16 and 56 in average daily physical activity counts (a subset of subjects).*
- *Change from Baseline to Weeks 16 and 56 in average daily minutes of moderate to vigorous physical activity (a subset of subjects).*
- *Change from Baseline to Weeks 16 and 56 in average daily minutes of bouts (sustained) moderate to vigorous physical activity (a subset of subjects).*
- *Change from Baseline to Weeks 16 and 56 in average daily step count (a subset of subjects).*

09001776e193181b056ApprovedApproved On: 08-10-2019 08:56 (GMT)

A valid day of monitoring will be defined as 10 or more wear hours in a 24-hour period as verified from accelerometer output. During Screening, a complete monitoring period will be defined as containing at least 1 valid weekend day of data and a minimum of 4 valid days of monitoring. During activity level monitoring between Week 14 and the Week 16 visit and between Week 54 and the Week 56 visit, a complete monitoring period will be defined as containing at least 2 valid weekend days of data and a minimum of 8 valid days of monitoring.

For the purposes of the MVPA endpoints, the three intensity levels of activity are defined as light (100 – <1,500 counts), moderate (1,500 – <6,500 counts), and vigorous (≥6,500 counts). The data will be further summarized as total daily time (minutes) for each intensity level.

A “bout” of moderate to vigorous activity is defined as 10 or more consecutive minutes above the moderate physical activity level threshold, with allowance for interruptions of 1 or 2 minutes below the threshold.

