The daily data for each endpoint will be calculated as indicated above. These daily scores will be used to calculate the score for Baseline, and Weeks 16 and 56 relative to the appropriate visit (ie, 7 days within the screening period for Baseline and 14 days prior to the Weeks 16 and 56 visits). All valid data will be used even if it exceeds the intended 7/14 days specified in the protocol.

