8.1.2. Analyses for Categorical Data

The number of days and amount (mg of acetaminophen/paracetamol) of rescue medication used per week will be analyzed using a negative binomial model with model terms of treatment group and covariates as described in [Section 6.4](#). In this model the error term is defined with a negative binomial distribution, and 'log' is used as the link function. Output from this analysis will be the estimated number/amount of rescue medication use per week in each treatment group, and (following the exponential back transformation) the ratio of rescue medication use for the treatment comparisons shown in [Section 4.1](#). The 95% CIs will be given for the estimates of both the individual treatment groups and the treatment group ratios.

The change from Baseline in the NIS will be analyzed using a Cochran-Mantel-Haenszel (CMH) test for 'row mean scores differ', using change from Baseline categories as the scores in the analysis, and stratified by the combined levels of the three stratification factors ([Section 6.4](#)). Output will show number and percentage of subjects whose NIS score worsened (change >0), improved (change <0) or had no change, in addition to the mean (with standard deviation) and median change, and minimum and maximum change. This analysis will be performed for the two treatment comparisons separately, and shown by visit and worst change (largest change from baseline to any post-baseline visit), and by last change (summary statistics only).

090017764931781b656\Approved\Approved On: 03-Oct-2019 08:56 (GMT)

The change from Baseline in the Patient's Global Assessment of Osteoarthritis to Weeks 2, 4, 8, 16, 24, 32, 40, 48, and 56 will also be analyzed using the CMH test and stratified by the combined levels of the stratification factors. Changes by each level of improvement will be summarized, as well as any improvement (change<0), and any worsening (change>0). For this analysis imputation for missing data will use mixed BOCF/LOCF, BOCF, and LOCF.

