Change from Baseline in LEAS to Weeks 4, 8, 16, 24, and 56, and worst post-baseline score.	ITT	CMH test	Treatment group [1]	LOCF (weeks 4, 8, 16, 24, and 56) and worst score	Secondary Endpoint Analysis
Change from Baseline in Accelerometry endpoints (daily minutes of physical activity, MVPA and bouts MVPA; daily step count; daily physical activity counts) to Weeks 16 and 56	Accelerometry analysis set	negative binomial	BL Score, BL Diary Average Pain, Index Joint (Knee/Hip), Highest KL grade (2, 3 or 4), NSAID cohort, Treatment Group	Observed	Secondary Endpoint Analysis
Change from Baseline in Accelerometry endpoints (daily minutes of physical activity, MVPA and bouts MVPA; daily step count; daily physical activity counts) to Week 56	Accelerometry analysis set	negative binomial	BL Score, BL Diary Average Pain, Index Joint (Knee/Hip), Highest KL grade (2, 3 or 4), NSAID cohort, Treatment Group	LOCF	Secondary Endpoint Analysis
Incidence of primary composite adjudication joint safety endpoint	ITT	Poisson model for risk difference (exposure-adjusted)	Exposure, exposure*treatment	Observed	Primary Joint Safety Analyses
Incidence of primary composite adjudication joint safety endpoint	ITT	Poisson model for risk ratio (exposure-adjusted)	Treatment group, offset by log-exposure	Observed	Secondary Joint Safety Analyses
Incidence of primary composite adjudication joint safety endpoint	ITT	Exact analyses for risk difference and ratio (percentage)	Treatment group	Observed	Secondary Joint Safety Analyses
Incidence of secondary composite endpoint, individual adjudication joint safety endpoints (RPOA-1, RPOA-2, RPOA-1/2, SIF, Primary ON, Pathological fracture), TJR, and TJR and any adjudication outcome	ITT	Poisson model for risk difference (exposure-adjusted)	Exposure, exposure*treatment	Observed	Secondary Joint Safety Analyses
Incidence of secondary composite endpoint, individual adjudication joint safety endpoints (RPOA-1, RPOA-2, RPOA-1/2, SIF, Primary ON, Pathological fracture), TJR, and TJR and any adjudication outcome	ITT	Poisson model for risk ratio (exposure-adjusted)	Treatment group, offset by log-exposure	Observed	Secondary Joint Safety Analyses

090017764931816561Approved/Approved On: 08-10-2019 08:56 (GMT)

09/01/2019 17:56:56 Approved On: 08/10/2019 08:56 (GMT)

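### The SAP names change from Baseline as the analysed accelerometry variable but pairs it with a negative binomial model, which gives no likelihood to negative values; it should state that the response is the Week 16/56 level

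*SAP*

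**What the plan says.** SAP 6.3.4 defines all five accelerometry endpoints as changes, for example "Change from Baseline to Weeks 16 and 56 in average daily minutes of moderate to vigorous physical activity". The same section then derives a value at each time point rather than a difference: "These daily scores will be used to calculate the score for Baseline, and Weeks 16 and 56 relative to the appropriate visit".

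Item 12 of SAP 8.2.2 first says that change will be calculated for the parameters. It continues "Summaries and analyses of these endpoints will use observed data for change from Baseline to Weeks 16 and 56", with LOCF added for Week 56, and then "These parameters will be analyzed using a negative binomial model using covariates of the corresponding Baseline accelerometry score". The remaining covariates are diary pain, index joint, Kellgren-Lawrence grade, NSAID cohort and treatment.

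The SAP 8.2.5 table has two accelerometry rows, one for observed data at Weeks 16 and 56 and one for LOCF at Week 56. Both open with "Change from Baseline in Accelerometry endpoints (daily minutes of physical activity, MVPA and bouts MVPA", and both give negative binomial as the method.

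SAP 8.1.2 is where the model is described ("In this model the error term is defined with a negative binomial distribution", with a log link), but only for the days and amount of rescue medication.

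Protocol 9.4.4.2 has the same sequence of sentences on change and on the model. It differs in two ways: it first numbers the five parameters as average daily levels, and it closes with "Estimated levels of each activity parameter will be shown for each treatment group, and the ratio (with 95% CI) for comparisons versus NSAID". Item 12 of the SAP does not carry that closing sentence over.

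**The concern.** A negative binomial variable takes the values 0, 1, 2 and so on. A change from Baseline is negative whenever a subject becomes less active. If the table and the analyses sentence of item 12 are followed literally, the likelihood does not exist once a single subject has a negative change, and in this population many will.

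The programmer then has to choose a repair, and the SAP offers two. One is to model the Week 16/56 level and report a ratio, as Protocol 9.4.4.2 implies. The other is ANCOVA on change, which SAP 8.1.1 names for continuous change-from-Baseline endpoints and which item 7 of SAP 8.2.2 uses for the WPAI:OA change scores. The first estimates a ratio of levels and the second a difference in mean change. They are different quantities and need not agree on significance. That choice should be settled before unblinding.

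**Working it through.** **Inputs (Protocol 9.1).** Moderate to vigorous activity averages about 24 minutes per day with SD 20; the Baseline to post-Baseline correlation is 0.75; the SD of change is taken as 14; there are 120 subjects per group, so 360 in all. The section states "Formal sample size calculation was not peformed for the actigraphy data collection", but it does give illustrative power.

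**Step 1: reproduce the plan's figures.**
- SD of change = 20 × √(2 × (1 − 0.75)) = 14.14, which the protocol takes as 14.
- Standard error of a difference = 14 × √(2/120) = 1.807.
- Two-sided 5% power for 5 minutes: 5/1.807 = 2.766; Φ(2.766 − 1.960) = 79.0%.
- For 6 minutes: 6/1.807 = 3.320; Φ(3.320 − 1.960) = 91.3%.

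The stated 79% and 91% reproduce. They refer to a difference in mean change, not to the ratio that a log-link negative binomial model returns.

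**Step 2: support of the model.** For any y below 0 the negative binomial probability is 0, so the log-likelihood contribution is minus infinity. One such subject is enough.

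**Step 3: how often change is negative.** The documents give no expected within-arm mean change, so a range is shown. With change normal with mean μ and SD 14, P(change < 0) = Φ(−μ/14).

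| Mean gain μ (min) | P(change < 0) | Expected of 360, if all provide data |
|---|---|---|
| 0 | 0.500 | 180 |
| 5 | 0.360 | 130 |
| 10 | 0.238 | 86 |
| 20 | 0.077 | 28 |

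A mean gain of 20 minutes is 20/24 = 83% of the quoted mean, and it still leaves about 28 negative values. Under the same assumptions, the chance of none among 360 is below 10⁻¹².

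**Step 4: which response fits.** Average daily minutes, counts and steps are never negative, so the level is within the range that the model allows. Having the Baseline score as a covariate and a ratio as the output also fits a level. If the comparator mean were 24 minutes (an assumption), differences of 5 and 6 minutes would correspond to ratios of 29/24 = 1.21 and 30/24 = 1.25.

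**Step 5: non-integer averages.** An average over several days is usually not a whole number, and neither document says how it enters a count model. In 200 simulated data sets (assumed lognormal levels, mean 24, SD 20), rounding moved the ratio by at most 0.008. For an assumed low-level endpoint (mean 6, SD 8, 30% zeros) it moved it by at most 0.034.

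**The case against.** The strongest reply is that the intended analysis is already legible. In item 12, change is calculated *for* the parameters, so the parameters are the levels. The model sentence repeats that same term and adjusts for the Baseline score. Protocol 9.4.4.2 numbers the parameters as levels and promises levels and a ratio, and SAP 6.3.4 derives a score at each visit. The labels in the 8.2.5 table are loose elsewhere: the WPAI:OA row omits change although item 7 analyses change, and the health care utilization row lists Weeks 56 and 64 where item 8 has Weeks 64 and 80.

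Much of this stands. A reader might infer that the SAP leaves these endpoints with no runnable analysis. The documents do not support that, because fitting the level is a fair reading of the model sentence and agrees with the protocol.

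What the reply does not remove is the conflict. The sentence stating that analyses use change is in the running text as well as the table, the endpoints themselves are defined as change, and the output sentence that would settle the matter is missing from the SAP. The default in SAP 8.1.1 and the power basis in Protocol 9.1 both point towards change.

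**Conclusion.** The point holds as a minor error of specification: the SAP's named response conflicts with its named model. That the model excludes negative values needs no assumption. The shares of 50% to 8% rest on normality, on the protocol's SD of 14 and on an assumed range of mean gains, and they apply to minutes of moderate to vigorous activity only. The documents give no comparable SD for the other four endpoints.

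Two larger conclusions might be drawn and should not be. The documents do not show that the negative binomial model is a poor choice for activity levels; the point is only that its response must be named. Nor does this touch the trial's main conclusions. The endpoints are secondary, are measured in about 360 of 3000 subjects, and lie outside the multiplicity procedure of SAP 4.2, which covers the co-primary endpoints and the key secondary endpoint. The co-primary and joint-safety analyses are unaffected.

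**What to change.** Before unblinding:

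- **SAP 8.2.2 item 12 and both accelerometry rows of 8.2.5:** state that the modelled response is the average daily level of each parameter at Week 16 and at Week 56 (observed data, plus LOCF at Week 56). The model is the log-link negative binomial of Section 8.1.2 with the covariates already listed, including the Baseline score.
- **Item 12:** bring in the protocol's output, that is, estimated levels by group and the ratio of each tanezumab group to NSAID with its 95% CI. Say that change from Baseline is summarized descriptively.
- **SAP 6.3.4:** add a note linking the change endpoints to this analysis of levels.
- **SAP 8.1.2:** add a cross-reference so that the model definition covers accelerometry as well as rescue medication.
- **Optional:** say how non-integer averages enter the model, for example by rounding. This would be a new rule, since neither document has one.

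The cost is a few sentences, two relabelled rows and a cross-reference. The model, covariates and LOCF rule stay as planned. No protocol amendment is needed: Protocol Section 9 lets the SAP modify the planned analyses and calls for an amendment only for major changes to the primary endpoint or its analysis.
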